Regarding differential clinical activity among the three CDK4/6i drugs, in pivotal studies not all molecules demonstrated a statistically significant benefit in overall survival (OS), which endpoint was only achieved for studies with ribociclib (MONALEESA-2, MONALEESA-3, MONALEESA-7 trials), while abemaciclib demonstrated this benefit only in the context of disease endocrine-resistant disease (MONARCH 2). 13,14,19 However, the efficacy of palbociclib, ribociclib and abemaciclib has never been directly compared in large clinical studies. In fact, the available published literature consists of small case series lacking sufficient power for efficacy comparisons, and available studies did not properly adjust for confounders to homogenize treatment cohorts. 54-58 Only three large real-world comparisons of the three CDK4/6i were available in literature, two of these was recently presented at international congresses; however, none of these two studies were published in full to date. Pantano F. et al conducted a comparison among the three CDK4/6 on a cohort of 1184 patients using propensity score weighting for covariate adjustment, showing abemaciclib and ribociclib to be associated with better PFS when compared to palbociclib in the endocrine-sensitive setting, while abemaciclib was associated with better PFS when compared to both ribociclib and palbociclib in patients with endocrine-resistant disease. However, this analysis was limited by the relatively low number of enrolled patients, especially in the group of patients treated with abemaciclib (n=158).⁵⁹ Another study presented at ASCO 2024 annual meeting included 1511 HR+/HER2- aBC patients treated with ET+CDK4/6i as first- or second-line of treatment, showing that fulvestrant plus ribociclib was associated with better PFS and OS when compared to both fulvestrant plus palbociclib and fulvestrant plus abemaciclib; no adjustment method was applied when comparing PFS among the three drug cohorts, despite significant imbalance in the three groups. 60 Finally, Gehrchen et al conducted a real-world comparison between the three molecules on data extracted from a national Danish dataset. In the context of first-line subgroup of patients (N = 1554), they found better outcomes in terms of rwPFS of ribociclib and abemaciclib compared to palbociclib, also when adjusting with some clinical co-variates. 61 However, the lack of availability of an appropriate amount of patients' characteristics, such as biological ones, did not allow a proper adjustment between groups and potentially not correcting the confounding bias related to drug attribution by oncologists. This kind of problem underlines the need of deeply annotated, comprehensive datasets to conduct proper and trustworthy statistical analyses in the real-world setting.

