Finally, also the use of immunotherapy could represent a potential option for pre-treated HR+/HER2- aBC. The phase 2 PACE trial demonstrated potential activity of the immune-checkpoint inhibitor avelumab plus fulvestrant compared with fulvestrant alone or the combination of fulvestrant and palbociclib, in patients with HR+/HER2- aBC progressing after first-line ET+CDK4/6i, with a statistically significant advantage in terms of PFS (8.1 months for triplet vs 4.6 for doublet vs 4.8 for Fulvestrant alone), opening an opportunity for immunotherapy in selected patients in this setting.⁸¹

Together, these data indicate that several therapeutic options are available, or may become available soon, for the treatment of HR+/HER2-aBC patients in different lines of therapy. However, few reliable predictive biomarkers actually exist for optimizing the treatment trajectory of individual patients and finally improving overall survival (OS). Since there is no accepted evidence on which is the best choice after CDK4/6i+ET for HR+/HER2-aBC patients, clinicians are left alone during the treatment decision, causing fragmentation in therapeutic practice between cancer centers and even among individual oncologists.

The importance of real world data (RWD) in HR+/HER2- aBC patients treated with ET+CDK4/6i

Recently, there has been a growing interest in observational real-world studies, due to their ability to observe the effects of a given treatment even outside the ideal clinical conditions that characterize RCTs. These types of studies also allow sub-analyses to be carried out in certain subgroups, usually underreported in RCTs, and Version 1.1, 01Aug2024

Pag. 10 di 32

to study biomarkers potentially useful for establishing treatment efficacy. This is particularly relevant in the context of established clinical settings, such as HR+/HER2- aBC patients who are candidates for first-line therapy, where it is difficult, in terms of ethics and pharmaco-economics, to conduct comparison prospective randomized trials to address specific clinical questions.

In this context, and in view of the long average duration of patients' exposure to this class of drugs, it is of primary importance to more accurately establish the real-world efficacy and toxicity of the three CDK4/6i.

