PALMARES-2 is a retrospective/prospective, observational, multicenter, population-based study, aiming at providing real-world evidences on HR+/HER2- aBC patients treated with first-line CDK4/6i plus ET.

The present study has the objective to collect data coming from different sources, i.e. RWD, medical images and biological samples, from patients treated with CDK4/6i as first-line of therapy for HR+/HER2- aBC. In consideration of the complexity of data collected and different objectives of the study, this master protocol foresees different sub-studies, which encompasses different methodologies for data collection, data extraction and analyses. The sub-studies will be described in the following sections.

[figure not shown]

Figure 1. PALMARES-2 graphical abstract. CBC: cell blood count; CT: computed tomography; ET+CDK4/6i: endocrine therapy plus cyclin-dependent kinase 4/6 inhibitor; FdG-PET: fluorodeoxyglucose positron emission tomography; FFPE: formalin-fixed paraffin-embedded; HE: hematoxylin-eosin; HR+/HER2- aBC: hormone receptor-positive, human epidermal growth factor receptor 2-negative advanced breast cancer; PD: progressive disease; RWD: real-world data.

(1) Real world data (RWD) PALMARES-2 sub-study

Objectives and endpoints of the sub-study:

Primary objectives:

- To test the difference in terms of OS between the group of patients receiving ribociclib and palbociclib;
- To test the difference in terms of OS between the group of patients receiving abemaciclib and palbociclib.

Secondary objectives:

- To test the difference in terms of OS between the group of patients receiving abemaciclib and ribociclib.
- To determine the real-world progression-free survival (rwPFS), time to next treatment or death (TTNT-D), time to chemotherapy or death (TTC-D) and OS in the real-world setting;
- To test the difference in terms of rwPFS between the group of patients receiving ribociclib and palbociclib;
- To test the difference in terms of rwPFS between the group of patients receiving abemaciclib and palbociclib;
- To test the difference in terms of rwPFS between the group of patients receiving abemaciclib and ribociclib;
- To test the difference in terms of TTNT-D between the group of patients receiving ribociclib and palbociclib;
- To test the difference in terms of TTNT-D between the group of patients receiving abemaciclib and palbociclib;
- To test the difference in terms of TTNT-D between the group of patients receiving abemaciclib and ribociclib;

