For the "Translational sub-study" purposes, tumor samples related to patients enrolled in the RWD sub-study will be considered. If multiple tumor samples are available, the ones to be used for the study has to be chosen as specified in the section "Translational sub-study". Tumor materials have to be shipped to the Sponsor center at the moment of the conduction of translational analyses, attributing the same pseudonymized code used for the other sub-study. The remaining unused tumor tissue will be sent back to the pathology laboratory at the end of the study.

Statistical considerations

Statistical design

Based on pivotal trials showing a statistically significant OS advantage for ribociclib and abemaciclib, but not for palbociclib in the endocrine resistant setting, and clinically meaningful OS advantage for ribociclib and abemaciclib, but not for palbociclib in the endocrine sensitive setting, we will hypothesize a difference of 20% in terms of OS between ribociclib versus palbociclib and between abemaciclib and palbociclib. To detect this difference with 80% power with a two-sided alpha error of 0.05, a sample size of 3258 patients reaching 977 OS events will be required. The prognostic role of CDK4/6i drug will be weighed for clinically and biologically relevant characteristics.⁸⁹

Since the number of patients enrolled in the other sub-studies depends on the sample size of the RWD sub-study, no formal statistical calculation has been performed for 2 to 5 PALMARES-2 sub-studies.

Statistical methods

Version 1.1, 01Aug2024

Standard descriptive statistics will be used to describe clinical and biological patients' characteristics. The median and interquartile range (IQR) were reported for continuous variables. Categorical variables were summarized as percentages of available data. To evaluate differences, in terms of clinic-pathological characteristics, among different CDK4/6i groups, we will use the Kruskal-Wallis Rank Sum test for

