continuous variables and the Chi-square and Fisher exact tests for categorical variables. Unpaired t-test will be used to compare numeric variables, at baseline and different timepoints. Classic survival analysis methods will be used to evaluate patient survival outcomes and survival curves will be obtained through the Kaplan–Meier method. Follow-up times will be estimated using the reverse Kaplan–Meier method. Multivariable analysis will be performed through Cox regression modeling to estimate the effects of covariates. To homogenize patients' characteristics among treatment groups, additional adjustment techniques will be eventually used, such as propensity score matching (PSM) and inverse probability of treatment weighting (IPTW). Estimated weights will be then incorporated into a weighted Cox regression model to estimate rwPFS. Area Under the ROC Curve (AUC) values of the models will be calculated using the Caret and pROC R package and compared using Delong's test.

Patients with missing outcome data will be excluded from the analysis. Covariates whose values will be missing in less than 20% were imputed by using the median or the mode value (for numerical or categorical variables, respectively), while covariates with missing values exceeding 20% will be excluded from the present analysis. 90 All statistical tests will two-tailed, and a p value (P) <0.05 was considered as significant. Statistical analyses will be performed using R software and R Studio (version 4.1.2).

Image omics and model generation methodology

Radiomics Methodology

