A team of four radiologists with experience on CT scan/PET images segmentation will identify the Volume Of Interest (VOI) through a semi-automated 3D segmentation process performed with Syngo.via software. An ad hoc designed segmentation protocol will be applied to homogenize the choice of CT/PET sequence on which to perform segmentation and the choice of the lesion to be segmented. Peritumoral area will be obtained through automated augmentation techniques (+5 mm, +10 and +15 mm); if the peritumoral area obtained crosses blood vessels, gas, bone, bile duct, or exceeded the organ edge, the contour will be manually modified to exclude this area. After image pre-processing through different techniques (e.g., gray discretization, intensity normalization, and voxel resampling), radiomic features will be extracted from VOIs and peritumoral areas using the PyRadiomics library in Python. In order to prevent signature overfitting, dimensionality of features is reduced before signature construction, firstly excluding features with high intraclass correlation coefficient and significantly different between the two outcome groups as assessed by one-way analysis of variance (ANOVA). Least absolute shrinkage and selection operator (LASSO) regression and/or Maximum Relevance Minimum Redundancy (MRMR) will be then used for the selection of features that will be included in the final model. The cohort will be split in a training (80%) and testing cohort (20%). Different standard classifiers, such as Random Forest, Multilayer perceptron, Logistic

Regression, Support Vector Machine, CatBoost, AdaBoost, XGBoost, will be trained and evaluated for this task. 91,92

Pathomics Methodology

Pathology slides will be digitalized with Leica Scanscope AT2 and stored as ".svs" files to obtain Whole Slide Images (WSIs). Hematoxilin and Eosin (HE) slides will be digitalized for pathomics purposes. WSIs will be analysed through Slideflow, a Python package that provides a unified Application Programming Interface for building and testing models for histopathology. After color normalization procedures, quantitative pathomics features will be extracted. Model creation and performance evaluation will follow the same methodology discussed in the "Radiomics" workflow. 93

Multimodal integration

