We will use several architectures, including logistic regression, classification and regression trees, random forest, multi-layer perceptron, gradient boosted trees (XGBoost), gradient boosting machines (LightGBM) and attentive tabular networks TabNet and we will compare their performance to heuristically decide on the best model choice for follow-up experiments. Our modelling experiments will include different combinations of input embeddings, with concatenation of each data stream permutation to produce fusion embeddings and train models using single-modality or multi-modality of input combinations. All models will be trained multiple times with multiple different data splits to repeat the experiments and compute average metrics and SDs. All defined models will be trained and tested to evaluate the advantage of multimodal predictive systems, as compared to single modality ones for the pre-established classification prediction. To assess model performance, different metrics will be used, including AUC, Sensitivity and Specificity, which will be calculated on the training set through 10-fold cross-validation and on the test set, which will be obtained by randomly splitting the entire cohort in a 80:20 way. The hyperparameter combinations of individual models, such as maximum depth of the trees, number of estimators and learning rate, will be selected within each training loop using a fivefold cross-validated grid search on the training set.^{94,95}

Since these complex models are considered as "black boxes", since they make decisions without clear reasoning, explainability techniques will be adopted to provide insights into how models make predictions, guaranteeing human interpretability. In particular, SHapley Additive exPlanations (SHAP) techniques will be used for both global and local explanations. ⁹⁶

Biological analyses methodology

Genomic analyses

A next generation sequencing (NGS) panel (Oncomine Comprehensive Assay Plus) will be used to perform analysis of various single-gene variants, such as single nucleotide variations (SNVs), indels, fusions, splice Version 1.1, 01Aug2024

Pag. 26 di 32

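### The random 80:20 split of a multicentre cohort never tests the prediction models at an unseen centre; secondarily, centre is not named in the adjustment of the OS comparison

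*Protocol*

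**What the plan says.** Master protocol study design describes a "retrospective/prospective, observational, multicenter, population-based study". Under Medical images collection and sharing, images are gathered at each centre and uploaded to a folder kept for that centre. Slides come from diagnostic biopsies and surgical specimens.

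**Model testing.** Radiomics Methodology divides the cohort into 80% training and 20% testing, and Pathomics Methodology follows the same workflow. Multimodal integration states that the test set is one "which will be obtained by randomly splitting the entire cohort in a 80:20 way", and repeats training over several splits to average the metrics. No section reserves a centre or an external cohort. The same pages do plan harmonisation: a segmentation protocol, intensity normalisation, voxel resampling, colour normalisation of slides, and one named slide scanner.

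**OS comparison.** Statistical design says: "The prognostic role of CDK4/6i drug will be weighed for clinically and biologically relevant characteristics". Statistical methods plans Cox regression, with propensity score matching or inverse probability weighting as possible additions to balance patient characteristics, and continues: "Estimated weights will be then incorporated into a weighted Cox regression model to estimate rwPFS". Centre is not named as a covariate, stratum, random effect or cluster, but no closed covariate list is given either.

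**The concern.** Scanner, acquisition settings and staining differ between hospitals, and so may prognosis. A model that partly recognises the hospital can then score well on test patients from the hospitals it was trained on, without that score carrying over elsewhere. The protocol wants tools that can be applied in clinical practice, so performance at a new centre is the quantity of interest, and the planned split does not estimate it. Averaging over several random splits does not help, because each split mixes centres in the same way.

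The OS question has a related structure. Treatment is not randomised. If centres differ both in which CDK4/6 inhibitor they tend to start and in survival, part of the centre difference can be attributed to the drug. The hypothesised effect is only 20%, so a modest shift would matter.

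**Working it through.** **1. Overlap of centres under the random split.** Input: the 80:20 ratio (Protocol, Multimodal integration). Treating patients as allocated independently, a centre with n patients falls in both sets with probability 1 − 0.8^n − 0.2^n.

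- n = 5: 1 − 0.3277 − 0.0003 = 0.67
- n = 10: 1 − 0.1074 = 0.89
- n = 20: 1 − 0.0115 = 0.99

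Only very small centres have an appreciable chance of falling wholly on one side.

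**2. How much centre identity could carry.** Assumption: the log odds of an early event vary normally between centres with SD s. Scoring each patient by the true risk of their centre, and nothing else, gives AUC ≈ Φ(s/√2).

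- s = 0.3: Φ(0.212) = 0.58
- s = 0.5: Φ(0.354) = 0.64
- s = 0.7: Φ(0.495) = 0.69

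A simulation with 20 centres and 3000 patients gave 0.58, 0.63 and 0.68. This shows what perfect knowledge of centre risk would yield. It does not estimate the optimism of an image model. For scale, the protocol calls an AUC of 0.77 notable in a published radiomic model (Unmet clinical needs section).

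**3. The plan's own figure for OS.** Statistical design gives 977 events in 3258 patients (977/3258 = 0.300), two-sided alpha 0.05 and 80% power. Schoenfeld: events = (1.96 + 0.8416)² / [p(1 − p)(ln HR)²]. With HR 1.20 and p = 0.41: 7.849 / (0.2419 × 0.03324), giving 977. HR 0.80 at 1:1 gives 631. The figure is therefore reproduced if 20% is read as HR 1.20 with a 41:59 allocation; both are inferred, not stated.

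**4. Omitting centre from the OS model.** All inputs are assumptions: 20 centres, 2172 patients in two arms (two thirds of 3258), about 34% events, true HR 1, 400 runs per cell. The Monte Carlo standard error near 5% is √(0.05 × 0.95/400) = 1.1 percentage points. r is the correlation between centre prognosis and centre drug preference. The Cox model ignores centre except in the last column.

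| Centre SD (log hazard) | Preference SD (logit) | r = 0: type I | r = +0.5: mean HR, type I | r = −0.5: mean HR, type I | Stratified by centre: type I over the three r |
|---|---|---|---|---|---|
| 0.1 | 0.5 | 6.0% | 1.02, 6.75% | 0.97, 6.5% | 5.75% |
| 0.1 | 1.0 | 5.25% | 1.04, 9.75% | 0.96, 8.5% | 3.5–6.0% |
| 0.2 | 0.5 | 7.75% | 1.05, 10.5% | 0.96, 10.5% | 6.25–7.5% |
| 0.2 | 1.0 | 8.5% | 1.08, 21.25% | 0.93, 19.75% | 4.25–6.5% |
| 0.3 | 0.5 | 7.5% | 1.07, 17.25% | 0.94, 16.0% | 5.0–6.75% |
| 0.3 | 1.0 | 11.75% | 1.12, 32.75% | 0.89, 37.25% | 5.25–6.0% |

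Stratified by centre, the mean HR is 0.99 to 1.01 throughout. At r = 0 there is no mean bias. In a separate run of 2000 replicates with centre SD 0.3 but no variation in drug preference, the unstratified test rejected 4.4%, so both kinds of centre variation are needed for inflation.

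**5. Price of including centre.** If centre explains a share ρ² of the variance in drug choice, the events needed are 977/(1 − ρ²): 1029, 1086, 1222 and 1396 for ρ² = 0.05, 0.10, 0.20 and 0.30. With events held at 977, power falls from 80.0% to 78.0%, 75.8%, 70.8% and 65.0% (HR 1.20, 41:59).

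**The case against.** On the split, the defence is that a random hold-out is ordinary internal validation, that the protocol does not claim performance at new hospitals, and that harmonisation and repeated splits are planned. The first two are true, but they concede that transfer is untested. Harmonisation is a real mitigation, yet its success is not observable from a split in which training and test patients share centres. It also stands that the AUC values in step 2 assume perfect knowledge of centre risk. A reader might infer that the reported AUC will in part measure recognition of the centre; nothing in the protocol shows that it will, only that the planned test could not tell.

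On the OS comparison the objection is stronger. A reader might infer that centre is excluded from the adjustment and that the primary p-values and hazard ratio are therefore wrong. The wording is open, and covariates, strata and clustered variances are commonly left to a statistical analysis plan, which is not at hand. Nor does the protocol say that the choice among the three first-line drugs varies by centre. Its remark about treatment choice "causing fragmentation in therapeutic practice between cancer centers and even among individual oncologists" concerns therapy after progression on CDK4/6 inhibitors. That supports a link between centre and OS through later lines, but not a link between centre and first-line drug. The nearest statement on drug choice, "potentially not correcting the confounding bias related to drug attribution by oncologists", criticises another study and speaks of oncologists, not centres.

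Finally, step 4 tested an unweighted Cox model with no patient-level confounding, so its clean result for stratification does not carry over in full to a weighted model or to one that pools small centres.

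**Conclusion.** The point about the split holds on the protocol's text. The method is fixed, most centres will sit on both sides of it, and performance at an unseen centre is not estimated anywhere. How far the planned AUC would exceed performance elsewhere cannot be stated from the documents.

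The point about OS is secondary and conditional. Centre is not named, although the sponsor knows it. Inflated type I error requires both drug preference and prognosis to vary by centre, and bias in the hazard ratio also requires the two to be correlated. Under the assumed ranges, type I error without centre is about 5% to 12% at zero correlation and 6.5% to 37% at a correlation of 0.5 in either direction, with mean hazard ratios from 0.89 to 1.12 when the truth is 1. The documents support none of these SDs or correlations, so the figures show what is possible. They are not an estimate for this study, and they do not establish that the primary analysis is biased.

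**What to change.** **Models (Radiomics, Pathomics, Multimodal integration).** Split by centre: hold out whole centres, or use leave-one-centre-out (internal-external) validation, grouping small centres. Report that as the main test performance and keep the random split as secondary. Images are already filed by centre, so only wording changes. The cost is an AUC that may be lower and will be less precise, since the number of held-out centres limits it.

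**OS comparison (Statistical design, Statistical methods).** Name centre in the OS models through a centre-stratified or shared-frailty Cox model, with centre-clustered standard errors when inverse probability weights are used. At the least, pre-specify this as a sensitivity analysis. The cost is that centres using a single drug contribute little and some power is lost, as step 5 illustrates. If small or single-drug centres are pooled, the grouping should be fixed in advance, because pooling can let between-centre differences back in. If a statistical analysis plan already does this, a cross-reference in the protocol is enough.

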Furthermore, breast cancer intrinsic subtypes, as evaluated by PAM50 transcriptomic profiles, were observed to differently benefit from CDK4/6i in combination with ET. In particular, basal-like tumors are associated with poor prognosis and refractoriness to the addition of CDK4/6i to ET alone, as observed in a retrospective pooled analysis across the MONALEESA phase III studies (mPFS 3.7 with ribociclib vs 3.6 with placebo).^{32,33}

Prognostic biomarkers in HR+/HER2- aBC patients treated with first-line CDK4/6i plus ET combinations

Despite the tremendous improvement in the prognosis of HR+/HER2- aBC patients, a minority (~10-15%) of patients treated with first-line ET+CDK4/6i still undergo early disease progression. This subgroup of patients could therefore benefit from treatment intensification, such as through the addition of a target therapy (e.g., PI3Ki, AKTi, mTORi, PARPi for selected populations), hormonal backbone enhancement (e.g., oral SERD), or even from the use of a completely different treatment strategy such as chemotherapy or novel antibody drug conjugates (ADCs). Conversely, another subgroup of patients demonstrated to derive long-term benefit from ET+CDK4/6i in pivotal trials, with 23.3% of patients enrolled in the MONARCH 3 trial still on treatment after a median follow up of 72 months. These patients could potentially benefit from tailoring treatment in terms of de-escalation, sparing unnecessary toxicities without negatively impacting on survival outcomes.

However, there are no studies conducted to date with the specific aim of identifying the subset of patients at high risk of early progression or, conversely, long-term benefit. Several clinical and biological factors demonstrated in clinical trials to have relevant impact on prognosis, and the addition of specific CDK4/6i differently improved prognosis across pivotal trials. Among these, endocrine resistance, presence of liver metastasis, tumor biology intended as luminal A- or B-like disease, menopausal status, de novo metastatic presentation, patient age and comorbidity.^{37–40} Mason et al conducted an individual-level analysis using

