- To test the association between blood lymphocyte counts at baseline, or their precocious ontreatment modifications (T1: 2 weeks after treatment initiation, and T2: before fourth cycle initiation, approximately 12 weeks after treatment initiation) and rwPFS, TTNT-D, TTC-D and OS of HR+/HER2- patients treated with first-line ET plus CDK4/6i;
- To evaluate the association between peripheral blood crude cell counts, namely whole blood cells, neutrophils, monocytes and platelets, as evaluated at baseline and as precocious on-treatment modifications, and patient rwPFS, TTNT-D, TTC-D and OS;
- To evaluate the association between baseline composite parameters, such as the Neutrophil-to-Lymphocyte ratio (NLR), the platelet-to-lymphocyte ratio (PLR), the monocyte-to-lymphocyte ratio (MLR), or the Pan-Immune Inflammation Value (PIV), and patient PFS;
- To evaluate the association between precocious on-treatment modifications (i.e., 2 weeks and ∼12 weeks after treatment initiation) of NLR, PLR, MLR and PIV, and patient PFS;
- To evaluate the association between HER2 status (HER2-low vs. HER2-0; HER2 2+ with negative ISH vs. HER2 1+ vs. HER2-0) in the primary tumor and rwPFS, TTNT-D, TTC-D and OS;
- To evaluate the association between HER2 status (HER2-low vs. HER2-0; HER2 2+ with negative ISH vs. HER2 1+ vs. HER2-0) in one metastatic site (subjected to biopsy before CDK 4/6 inhibitor initiation), and rwPFS, TTNT-D, TTC-D and OS;
- To explore pattern of progression of HR+/HER2- aBC after ET plus CDK4/6i treatment;
- To test the effect on rwPFS, TTNT-D, TTC-D and OS of mastectomy in patients with *de novo* HR+/HER2- aBC.

Study Population

Inclusion criteria:

- Pre- and Post-menopausal patient (woman OR man)
- Age≥18 years
- Diagnosis of aBC. HR+/HER2- aBC, as defined as at least 1% estrogen receptor (ER) and/or progesterone receptor (PgR) positivity at IHC. HER2 negativity is defined on the basis of an IHC score of 0, 1+, or 2+ with absence of gene amplification at in situ hybridization (ISH) analyses.
- Have received or are candidate to receive treatment with palbociclib, ribociclib or abemaciclib in combination with endocrine therapy as first-line treatment for HR+/HER2- aBC.

Exclusion criteria:

- Less than 3 months of follow up from the CDK4/6i start to the date of data cut-off;
- Have received CDK4/6i as monotherapy;
- Have received CDK4/6i as adjuvant treatment for localized disease.

Data collection

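### The under-20% median-imputation rule does not exempt on-treatment markers; applied to the week-12 blood counts, it would give early progressors a value that their own event made impossible

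*Protocol*

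**What the plan says.** Protocol, Statistical considerations, Statistical methods:
- Below the threshold: "Covariates whose values will be missing in less than 20% were imputed by using the median or the mode value".
- Above it: "while covariates with missing values exceeding 20% will be excluded from the present analysis".
- The only rule that removes patients: "Patients with missing outcome data will be excluded from the analysis".
- The model: "Multivariable analysis will be performed through Cox regression modeling to estimate the effects of covariates".

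Protocol, RWD sub-study, secondary objectives: "To test the association between blood lymphocyte counts at baseline, or their precocious ontreatment modifications", where the later time point is "T2: before fourth cycle initiation, approximately 12 weeks after treatment initiation". Lymphocytes and the other crude cell counts are related to rwPFS, TTNT-D, TTC-D and OS; changes in NLR, PLR, MLR and PIV are related to PFS.

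Two further places bear on the point. The exclusion for less than 3 months of follow-up is measured from CDK4/6i start to data cut-off, so it is a calendar condition and does not require a patient to be event-free at week 12. The RWD sub-study's Data collection section schedules blood counts at baseline, day 15, day 30 and progression, without a week-12 draw. The toxicity sub-study does have a draw before cycle 4, but lists it for liver and kidney parameters.

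The protocol mentions no landmark, delayed entry or time-dependent term for on-treatment markers.

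**The concern.** A patient who progresses, stops or dies before cycle 4 has no T2 count. The value was not merely left unrecorded: it never came into being, and the reason is the outcome or something close to it. Such a patient has an observed outcome, so the missing-outcome rule keeps the patient in. If the imputation rule is then applied to the T2 marker, an event that has already happened is analysed against a typical marker level taken from patients who got past week 12.

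This differs from median imputation of an ordinary confounder, because the filled variable is the marker under test and its missingness is tied to the endpoint. At stake is whether the T2 associations for lymphocytes, the other cell counts and the composite scores can be read at face value.

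**Working it through.** The protocol gives no figure of its own on this point. Its one computed design figure (977 OS events in 3258 patients) concerns the drug comparisons and does not enter here.

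**1. How many patients have an event before T2?** Twelve weeks is 84/30.44 = 2.76 months. With exponential rwPFS (assumption), the share is 1 − 2^(−2.76/median). The medians are those of the earlier first-line HER2 analysis described in the background.
- Median 32.3 months: 1 − 2^(−0.0854) = 5.8%.
- Median 23.6 months: 1 − 2^(−0.1169) = 7.8%.

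The background also says that "a minority (~10-15%) of patients treated with first-line ET+CDK4/6i still undergo early disease progression", without defining early. Placing 12.5% before week 12 is used below as an upper scenario; that is an assumption. For T1, taking day 15 (0.49 months), the same formula gives about 1.0-1.4%.

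**2. Does the under-20% branch apply?** Event-driven missingness alone stays below 20%, but the rule turns on total missingness. The threshold is crossed once the unrecorded share among patients still event-free at week 12 exceeds:
- (0.20 − 0.058)/(1 − 0.058) = 15%, or
- (0.20 − 0.078)/(1 − 0.078) = 13%.

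With no week-12 draw in the schedule, either branch is possible.

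**3. What does imputation do to the estimate?** Cox models were simulated with 1500 cohorts per scenario and N = 2000 (the expected size at the first cut-off). Censoring was uniform over 3-60 months. T2 was missing if the event came before week 12, plus 3% at random, giving total missingness of about 9% and 15%. Missing values were set to the median. The early-event shares were 6.6% (median 28 months, between the two above) and 12.5%. The hazard ratio of 0.83 is the one reported for the early lymphocyte change in first line. That change was measured at 2 weeks and its scale is not given, so using it per SD at T2 is an assumption.

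| Marker and true effect | 6.6% early | 12.5% early |
|---|---|---|
| Continuous, symmetric, HR 1.00 | 1.00 (p<0.05 in 3%) | 1.00 (2%) |
| Continuous, symmetric, HR 0.83 per SD | 0.851 | 0.867 |
| Continuous, right-skewed, HR 1.00 | 0.972 (12%) | 0.949 (32%) |
| Continuous, right-skewed, HR 0.83 | 0.823 | 0.817 |
| Median split, HR 1.00, ties high | 1.29 (98%) | 1.55 (100%) |
| Median split, HR 1.00, ties low | 0.78 (98%) | 0.65 (100%) |
| Median split, true HR about 0.74, ties high | 1.01 | 1.24 |
| Median split, true HR about 0.74, ties low | 0.60 | 0.51 |

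For the symmetric continuous marker, the log hazard ratio shrinks by 1 − ln 0.851/ln 0.83 = 13% and 1 − ln 0.867/ln 0.83 = 23%. For the skewed marker (log-normal, sigma 0.5) with no effect, rejection rises to 17% and 51% at N = 3258.

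**4. After the change.** A week-12 landmark in event-free patients with a measured T2 gives HR 1.00 with 4-6% rejection under no effect, and recovers 0.83 when that is true. Omitting patients without a measured T2 gives the same estimates, because everyone with a simulated T2 value is event-free at week 12.

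**The case against.** The strongest objection is that covariates may mean adjustment variables only. The background describes the earlier lymphocyte study in those terms: covariates were selected to adjust the role of the blood counts, which were the markers. A broad reading would also discard any marker missing in more than 20%, which could cancel objectives on genomic alterations and on HER2 in biopsied metastases. This stands as a reason not to say that the protocol orders T2 to be imputed. It does not remove the problem: the same section says the Cox model estimates the effects of covariates, and nothing limits the rule to adjusters.

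Second, the under-20% condition is not established, because the schedule has no week-12 draw. This stands; the concern is conditional on it.

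Third, a reader might infer from the median-split rows that the T2 analyses will produce strong false findings. The documents do not support that. The protocol specifies no median split, and the direction of the bias reverses with the handling of ties. Nor does a continuous marker always bias towards no effect: the skewed marker with a true effect was slightly exaggerated.

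Fourth, landmarks are often left to a statistical analysis plan, which is not available here. Their absence alone would be no finding. The finding is that a rule which the protocol does state has no exception where it needs one.

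**Conclusion.** The concern holds in conditional form. If the rule is applied to T2 markers and total T2 missingness is under 20%, about 6-8% of patients enter the rwPFS analysis with a T2 value that their own event ruled out. For a continuous symmetric marker the result is attenuation (0.83 to about 0.85-0.87) with no false positives. For a skewed marker it is a modest false association. The bias is large only if the marker is cut at its median. If T2 missingness exceeds 20%, the rule removes the marker and the T2 objectives cannot be met.

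These sizes rest on exponential or piecewise-exponential event times, the assumed per-SD effect, and the assumed share of early events. For OS, only deaths before week 12 count as early events, so the effect is smaller, although patients who progress and stop before cycle 4 would still be imputed. For T1 it is small.

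A reader might infer that the main result is at risk. It is not: the T2 markers belong to secondary biomarker objectives, and this point does not affect the primary OS comparisons between drugs.

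**What to change.** In Statistical methods, limit the median or mode rule to baseline adjustment covariates. Add that on-treatment markers are not imputed, and that T2 markers are analysed from a week-12 landmark, in patients who are event-free for the endpoint in question and have a measured value, with time counted from the landmark. Treat T1 in the same way from day 15. Reconcile the blood-count schedule in Data collection with the T2 objectives, so that it is clear whether a week-12 count is collected.

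The cost is two or three sentences. The T2 analyses lose about 6-12% of patients (5.8-7.8% on the protocol's medians, 12.5% in the upper scenario), plus those whose T2 value was not recorded. The result then applies to patients who are event-free at the landmark, and the report should say so.
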